6 STATISTICAL METHODOLOGY AND ANALYSES

6.1 General Considerations

All analyses will be performed using SAS® Version 9.4 or higher. All data collected on eCRFs, diaries (from ePRO), and from clinical laboratory evaluations will be grouped and listed by treatment group, subject, visit, date and time, as feasible. Summary tables will be presented by population as appropriate. Descriptive summaries of categorical outcomes will include the number and proportion of subjects. Descriptive summaries of quantitative measures will include the number of subjects, mean, standard deviation (SD), median, minimum, and maximum, or as appropriate. In descriptive summary tables, if needed, the geometric mean will be calculated as the nth root of the resulting product of the values, and the coefficient of variation (in percent, %CV) will be calculated as 100* (SD/[arithmetic mean]).

Arithmetic means, SDs, and geometric means will be reported with two significant figures more than the reported values. Median, minimum and maximum values will be reported with the same accuracy as the reported source data. The %CV will be rounded to 1 decimal place.

Denominators of percentage of subject calculations will be based on the number of subjects in the treatment group and selected population unless otherwise specified.

In the event there are multiple results at a given visit and/or time point, the following logic will be applied for purposes of summarization by visit or time point: for pre-dose measurements and selection of a baseline value, the most recent non-missing result will be used, preferably the result recorded on Day 0 (the day prior to first administration of study drug), if available; for post-dose measurements, the earliest of the results will be selected. If multiple laboratory results are available for the same date and time and the discrepancy cannot be resolved, then the arithmetic mean of the results will be used unless specified in the data management plan or data handling conventions finalized before breaking the study randomization blind. All subjects entered into the clinical database will be included in subject data listings.

6.2 Handling of Missing Values

For the primary efficacy endpoint based on achievement of serum 25D level \geq 50 ng/mL at Day 14, missing results due to intercurrent illness, hospitalization, or death will be imputed as lack of achieving the targeted serum 25D levels. For the time-to-event primary efficacy endpoint based on aggregate symptom scores, the analysis is based on the proportion of subjects resolved over the total population. Missing scores occurring prior to resolution are considered as lack of resolution and kept in the denominator. This should provide a conservative estimate of the proportion resolved. Missing results after the first day of achieving a score of \leq 5 and followed by up to 5 days with score \leq 5, as defined in Section 5.2 for determining resolution, will not be imputed as lack of resolution.

For the time-to-event secondary efficacy endpoint based on aggregated symptom scores, the analysis is based on the proportion of subjects resolved over the total population. Missing scores occurring prior to resolution are considered as lack of resolution, and kept in the denominator, but missing results after the first day of achieving a score of ≤ 5 , and followed by up to 5 days with score ≤ 5 , provided that no individual score is ≥ 1 , as defined in Section 5.2 for determining resolution, will not be imputed as lack of resolution.

Similarly, for individual symptom scores, missing results prior to resolution of symptoms due to intercurrent illness, hospitalization, or death will be imputed as lack of resolution, and missing results after the first day of achieving a score of ≤ 1 and followed by up to 5 days with score ≤ 1 , as defined in Section 5.2 for determining resolution, will not be imputed as lack of resolution. This strategy is appropriate given the consistent trend in symptoms toward improvement over time, as generally observed in blinded data from this ongoing study.

For subjects who have achieved resolution of symptoms, missing daily symptom scores beyond the time of resolution will not be imputed. Subjects are instructed to report any symptoms that recur after resolution.

If responder status is not determinable for subjects with missing serum 25D results used in the efficacy analyses, responder status will be imputed using multiple imputation. The missing serum 25D results will be imputed 50 times to generate 50 complete data sets by using the SAS procedure MI using the logistic regression method with adjustment for covariates including treatment group, gender, age, race, dosing compliance and baseline and other serum 25D concentration determinations. The seed used will be 201901. Each of the 50 complete datasets will be analyzed using a Chi-square test and the SAS MIANALYZE procedure will be used to generate valid statistical inferences by combining results from the 50 analyses using Rubin's formula. No other efficacy data will be imputed.

The secondary endpoints based on incidence will not be imputed. These endpoints, for example hospitalization or mechanical ventilation, will either occur, or will be assumed not to have occurred. Since these items require clinical care, the occurrence will likely not go unreported. If there are more than 10% of subjects who are truly missing and lost to follow up, a tipping point approach will be used, first assuming that none of the events occurred in the missing subjects, and then if all missing subjects had the event. If there is a difference based on these extremes, the number of missing subjects assumed to have the event will be increased by 2 in the treated group, while holding the incidence in the placebo group as observed, until the tipping point is found. Missing values from the quality-of-life components of FLU-PRO Plus[©] questionnaire will not be imputed. The analysis of these items will be based on observed cases only with resolution requiring at least a three-day duration, as defined in Section 5.2.

The number of days with missing FLU-PRO Plus[©] questionnaires per subject will be summarized as the total number of missing as well as the number missing before and after resolution.

Adverse events (AEs) with missing onset date will be treated as treatment-emergent adverse events (TEAEs) and missing onset date will be imputed as Day 1, unless the event end date indicates that the event resolved prior to the administration of the investigational study drug. In this case, it will be documented in medical history. AEs with partial onset date will similarly be treated as TEAEs unless the partial onset date or end date of the event is complete enough to indicate that the event started or resolved prior to the administration of the investigational study drug, in which case it will be documented in medical history.

If an AE has missing severity or relationship to study drug, the missing severity will be set to severe and the missing relationship will be set to definitely related in all summary tables.

For the purpose of inclusion in prior or concomitant medication tables, incomplete medication start and stop dates will be imputed and then categorized into prior or concomitant medication categories.

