5.2 Description of Placebo Capsules

Dosage form:	Soft gel capsule	
Dose strength:	0 mcg calcifediol ER capsule	
Product description:	Blue oval capsules printed single-sided, centered with the logo O in white. Each bottle contains 30 capsules.	
Active component:	None	
Non-active components:	Paraffin wax, mineral oil, mono- and diglycerides, dehydrated alcohol, lauroyl polyoxylglycerides, butylated hydroxytoluene, hypromellose, modified starch, carageenan, sodium phosphate dibasic, sorbitol and sorbitan solution, FD&C Blue #1, titanium dioxide, medium chain triglycerides (coconut oil) and ink (white, which may contain titanium dioxide, isopropyl alcohol, propylene glycol, hydroxypropylmethyl cellulose 2910)	
Storage conditions:	20-25°C (68-77°F); excursions allowed to 15°C to 30°C (59°F to 86°F); protect from light and heat	

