9.2 Missing Data

For the primary endpoint based on achievement of serum 25D level \geq 50 ng/mL at Day 14, missing results due to intercurrent illness, hospitalization or death will be imputed as lack of achieving serum 25D levels. For the time-to-event primary efficacy endpoint based on aggregated symptom scores, the analysis is based on the proportion of subjects resolved over the total population. Missing scores occurring prior to resolution are considered as lack of resolution and kept in the denominator. This should provide a conservative estimate of the proportion resolved. Missing results after the first day of achieving a score of \leq 5 and followed by up to 5 days with score \leq 5, as defined in Section 9.10.1 for determining resolution, will not be imputed as lack of resolution.

For the time-to-event secondary efficacy endpoint based on aggregated symptom scores, the analysis is based on the proportion of subjects resolved over the total population. Missing scores occurring prior to resolution are considered as lack of resolution, and kept in the denominator, but missing results after the first day of achieving a score of ≤ 5 , and followed by up to 5 days

Protocol CTAP101-CL-2014	
CTAP101 (calcifediol) Extended-release Ca	psules

with score ≤ 5 , provided that no individual score is ≥ 1 , as defined in Section 5.2 for determining resolution, will not be imputed as lack of resolution.

Similarly, for symptom scores, missing results prior to resolution of symptoms due to intercurrent illness, hospitalization, or death will be imputed as lack of resolution, and missing results after the first day of achieving a score of ≤ 1 and followed by up to 5 days with score ≤ 1 , as defined in Section 9.10.1 for determining resolution, will not be imputed as lack of resolution. This strategy is appropriate given the consistent trend in symptoms toward improvement over time, as observed in blinded data from this ongoing study.

For subjects who have achieved resolution of symptoms, missing daily symptom scores beyond the time of resolution will not be imputed. Subjects will be instructed to report any symptoms that recur after resolution.

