The time to resolution is defined as the number of days from Day 1 (study drug initiation) to the first day of achieving the ≤ 5 score for a minimum of three consecutive days. The number of days to resolution will be determined by the first two successive qualifying scores which span a minimum of three consecutive days, provided that no score greater than 5 is recorded between the two qualifying scores. For clarity, resolution will be considered as having been achieved if two successive aggregate scores of ≤ 5 are recorded on the first day of this period and on a subsequent day that is at least two days (but not longer than 5 days) later even if no score has been recorded between the two days.

On each day during the study, subjects will record once daily (during a 24-hour period starting in the evening before the subject goes to sleep) the severity of COVID-19 symptoms using the FLU-PRO Plus[©] questionnaire.

[figure not shown]

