5.3 Secondary Efficacy Endpoints

The secondary endpoints are:

- 1. The number of days to resolution of five symptoms (trouble breathing, chest congestion, dry or hacking cough, body aches and pains, and chills and shivering), as measured by the FLU-PRO Plus[©] questionnaire, with resolution defined as the first aggregate symptom score of ≤5 which is maintained for a minimum of three consecutive days, with no individual symptom score >1:
- 2. Resolution, defined as the first score of ≤5 which is maintained for a minimum of three consecutive days (without subsequent relapse), for the aggregate five COVID-19 symptoms (trouble breathing, chest congestion, dry or hacking cough, body aches and pains, and chills and shivering) and for each individual symptom, defined as a score of 0 or 1, as measured by the FLU-PRO Plus[©] questionnaire as of Day 10;
- 3. Incidence of emergency room/urgent care visits;
- 4. Incidence of oxygen saturation below 94% (or requirement for supplemental oxygen);
- 5. Incidence and duration of hospitalizations;
- 6. Incidence of requirement for mechanical ventilation;
- 7. Mortality rate (as incidence);
- 8. Severity and duration of COVID-19 illness as evidenced by quality-of-life measures including ability to perform usual activities and opinion of overall health status, using the FLU-PRO Plus[©] questionnaire; and,
- 9. Clinical course of COVID-19 as a function of serum 25D concentrations of <50 ng/mL, 50 to 100 ng/mL and >100 ng/mL at Days 7, 14, 21 and 28, defined as the proportion of subjects in each treatment group with a total score of ≤ 5 for the selected five COVID-19 symptoms (trouble breathing, chest congestion, dry or hacking cough, body aches and pains, and chills and shivering) using the FLU-PRO Plus[©] questionnaire.

Endpoint items 3-7 are all based on incidence over the entire 42 day study period.

Once daily (during a 24 hour period starting in the evening before bedtime), subjects will record their ability to perform usual activities and their opinion of overall health status in an electronic diary using FLU-PRO[©] Plus questionnaire.

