6.10.2 Secondary Efficacy Endpoints

The following secondary endpoints will be tested statistically with methods described below, and the resulting nominal p-value will be reported for evaluation:

1. The number of days to resolution of five symptoms (trouble breathing, chest congestion, dry or hacking cough, body aches and pains, and chills and shivering), as measured by the FLU-PRO Plus[©] questionnaire, with resolution defined as the first aggregate symptom score of ≤5 which is maintained for a minimum of three consecutive days (see Section 5.2), with no individual symptom score >1;

- 2. Resolution, defined as the first score of ≤5 which is maintained for a minimum of three consecutive days (without subsequent relapse), for the aggregate five COVID-19 symptoms (trouble breathing, chest congestion, dry or hacking cough, body aches and pains, and chills and shivering) and for each individual symptom, defined as a score of 0 or 1, as measured by the FLU-PRO Plus[©] questionnaire as of Day 10;
- 3. Incidence of emergency room/urgent care visits;
- 4. Incidence of oxygen saturation below 94% (or requirement for supplemental oxygen);
- 5. Incidence of hospitalizations (mean duration of hospitalization will also be presented);
- 6. Incidence of requirement for mechanical ventilation; and,
- 7. Mortality rate (as incidence).

Endpoints listed will be summarized. For the analysis of the 34 individual symptoms assessed by the FLU-PRO Plus[©] questionnaire, a threshold of ≤1 is appropriate because it describes minor symptom severity (at worst "a little bit") which seems unlikely to presage a poor outcome. Analysis of the resolution of individual symptoms will be performed using a logistic regression, with baseline symptom score, baseline 25D level, and body weight as covariates. Analysis of the secondary endpoints based on incidence will be performed with a Chi-square test. Mean duration will be analyzed with ANCOVA. Mortality will be analyzed as incidence, with logistic regression with baseline symptom score, baseline 25D level and body weight as covariates. Rates only will be reported if there are too few deaths to be formally analyzed.

[figure not shown]

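### The missing-data rule for secondary endpoint 1 uses an item limit of ≥ 1, while the endpoint itself allows items of 1, so the SAP supports two derivations of the resolution day

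*SAP*

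**What the plan says.** **Endpoint definition.** SAP 5.3 item 1 asks for an aggregate score of 5 or less held for at least three consecutive days, "with no individual symptom score >1". Protocol 3.4.2 and 9.10.2 use the same limit. SAP 6.10.2 repeats it and adds a pointer: "minimum of three consecutive days (see Section 5.2), with no individual symptom score >1".

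**Gap rule.** SAP 5.2 accepts two qualifying aggregate scores at least two and not more than five days apart, "even if no score has been recorded between the two days". Its only condition on what lies between them is that no aggregate score above 5 is recorded. It sets no condition on individual items. Protocol 9.10.1 contains the corresponding rule.

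**Missing-data rule.** SAP 6.2 has a separate paragraph for the time-to-event secondary endpoint on the aggregate score. Only endpoint 1 fits that description. Blanks after the first qualifying score are not imputed as lack of resolution, "provided that no individual score is ≥ 1", and Section 5.2 is cited as the source. Protocol 9.2 has the same text, the same symbol and the same section number.

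**Neighbouring text.** The next paragraph of SAP 6.2, on individual symptoms, protects blanks "after the first day of achieving a score of ≤ 1 and followed by up to 5 days with score ≤ 1". In Protocol 9.2 the paragraphs on either side read "as defined in Section 9.10.1 for determining resolution"; only the endpoint 1 paragraph cites 5.2.

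**The concern.** One item limit defines the endpoint and a stricter one governs its missing days. With no item ≥ 1, all five items must be 0. With no item > 1, each may be 0 or 1.

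A programmer working from SAP 5.3, 6.10.2 and 5.2 would bridge a blank between two qualifying scores that contain an item of 1. A programmer working from SAP 6.2 as written may refuse to. Neither would be departing from the SAP, and the precedence clause in SAP 1 only ranks the SAP over the Protocol.

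The section cited for the rule does not settle it. SAP 5.2 has no item condition, and Protocol 5.2 is headed "Description of Placebo Capsules". The Protocol synopsis (Statistical Analyses, secondary endpoint 1) repeats that pointer.

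At stake are the event times, and possibly the event status, of some subjects in Tables 14.2.2.1 and 14.2.2.2. The choice should not be left open until the data are unblinded.

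**Working it through.** The plan gives no figure to reproduce here, and no diary-missingness rate. The check compares the two limits and then derives the resolution day both ways.

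**Step 1: what each limit admits.** For five items:
- no item > 1: 2^5 = 32 score patterns, with aggregates from 0 to 5;
- no item ≥ 1: 1 pattern, all zeros.

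The missing-data rule thus drops 31 of the 32 patterns that the endpoint accepts.

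**Step 2: the two derivations.**
- *Gap rule* (SAP 5.2, with the item limit of SAP 5.3): the first recorded qualifying day that has another qualifying score 2 to 5 days later, blanks allowed between.
- *Literal SAP 6.2*, for a subject with an item at 1: the first of three consecutive recorded qualifying days. This takes an unprotected blank to break the run. SAP 6.2 does not say so. It is an inference from the treatment of missing scores, worded for the primary endpoint as "Missing scores occurring prior to resolution are considered as lack of resolution and kept in the denominator" and in near-identical words for endpoint 1.

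**Step 3: worked diaries.** Every recorded score from Day 5 on qualifies. At least one item stays at 1, except that in the third diary Days 12 to 14 are all zeros.

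| Recorded days | Gap rule | Literal 6.2 |
|---|---|---|
| 5, 7, 8, 9 | Day 5 | Day 7 |
| 5, 6, 7, 9, 10 | Day 5 | Day 5 |
| 5, 8, 11, 12, 13, 14 | Day 5 | Day 11 |
| 5, 8, 11, then nothing | Day 5 | not resolved |

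In the second row Days 5 to 7 are complete, so the blank on Day 8 is irrelevant.

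**Step 4: all blank patterns.** Let D be the first qualifying day. Let each of D+1 to D+4 be blank or recorded (2^4 = 16 patterns), with a complete diary from D+5, all recorded scores qualifying and an item at 1. The gap rule gives day D in all 16. The literal reading gives:

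| Delay (days) | 0 | 2 | 3 | 4 | 5 |
|---|---|---|---|---|---|
| Patterns | 4 | 1 | 2 | 3 | 6 |

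The sum is 4 + 1 + 2 + 3 + 6 = 16. The 4 patterns without delay are those with D+1 and D+2 both recorded. The other 12 are later. These are counts of patterns, not probabilities or bounds.

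**The case against.** **It is an evident slip.** Every statement of the endpoint says > 1, the next paragraph of SAP 6.2 uses ≤ 1, and SAP 6.10.2 justifies ≤ 1 as minor severity. This stands as evidence of intent. It does not remove the fault: the symbol is the same in both documents and the cited section does not correct it. One supporting argument fails. It is said that ≥ 1 must be wrong because it makes the aggregate limit of 5 redundant, but five items of at most 1 sum to at most 5, so > 1 makes it redundant too.

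**The delay is not in the documents.** SAP 6.2 says which blanks are protected, not that the others break a run. Blanks after the first qualifying day are arguably not prior to resolution at all. This is fair. The conflict between the limits needs no inference; the delay does.

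**The pattern count depends on the gap length.** The sensitivity analysis in SAP 6.10.1 speaks of up to three missing days. With that limit the gap rule gives day D in 14 of 16 patterns, and the readings agree in 5 rather than 4. The count used here follows the limit stated in SAP 5.2. The alternative changes the counts and leaves the conflict in place.

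**The SAP pointer to 5.2 may mean only the gap rule.** That is a natural reading, and on it the SAP pointer is not wrong in itself. It still leaves the item limit without a source. The Protocol's pointers to 5.2 are wrong on any reading, though of little consequence because the SAP governs the analysis.

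**Conclusion.** The concern holds, as a minor one. The item limit in SAP 6.2 and Protocol 9.2 contradicts the definition of secondary endpoint 1, and SAP 6.10.2 sends the endpoint to a gap rule without that limit. That much follows from the text alone.

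The effect on a subject's resolution day rests on the inference that an unprotected blank breaks the three-day run, and on later recorded scores continuing to qualify; a later item above 1 could change the delay. Complete diaries, subjects with all items at 0, the primary endpoint and its alpha are unaffected. The rule is the same in both arms and the p-value is nominal. The effect in this trial cannot be computed without a diary-missingness rate, and no effect on a hazard ratio or p-value is claimed.

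**What to change.** Before database lock and unblinding:

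1. Change ≥ 1 to > 1 in the endpoint 1 paragraph of SAP 6.2 and of Protocol 9.2.
2. In that paragraph, cite SAP 5.3 item 1 (Protocol 3.4.2 item 1) for the item condition and SAP 5.2 (Protocol 9.10.1) for the gap rule.
3. Replace Section 5.2 with Section 9.10.1 in that paragraph of Protocol 9.2 and in the Protocol synopsis entry for this endpoint.
4. Preferably add one sentence to SAP 6.10.2 stating that the item condition applies to every recorded score between the two qualifying scores. SAP 5.2 restricts only the aggregate there.

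The cost is one character in each document, a few cross-references and, if adopted, one sentence. No new data are needed.

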6.9 Removal of Subjects from the Study or Study Drug / Stopping Criteria

The investigator may discontinue a subject from study drug treatment for any of the following reasons:

- A major protocol deviation occurs;
- A serious or intolerable AE occurs;
- The subject has a confirmed pregnancy;
- A clinically significant change in a laboratory parameter occurs (eg, increase in serum calcium above upper limit allowed); and,
- A clinically significant change in ECG at Visit 3 occurs as compared to baseline (eg, prolongation of QT interval).

The investigator may withdraw a subject from the study for any of the following reasons:

- The subject requests to be discontinued from the study (withdraws consent); or,
- The subject is lost to follow-up.

Subjects who develop severe (CTCAE \geq 3) abnormalities (low or high) of serum phosphorus, uric acid or plasma iPTH will be withdrawn from study drug treatment.

Enrollment of subjects into the study will be paused if mortality in the treatment arm is $\geq 7\%$ higher compared to the placebo arm until the DSMB makes an assessment about causality, and may resume once the DSMB deems it acceptable to continue (if applicable).

No subject replacement is planned. All subjects withdrawn from treatment will continue in the study until study completion and perform all assessments unless consent is withdrawn. The investigator will be requested to make all reasonable efforts to obtain clinical status at FU.

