7.10 Days 29-41

- No study site visits.
- Subject will assess and record in the diary each day at bedtime the severity of COVID-19 symptoms and quality-of-life using the FLU-PRO Plus[©] questionnaire.

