The severity, duration and clinical course of COVID-19 illness will be compared between treatment groups by analyzing changes in quality-of-life assessments recorded on the FLU-PRO Plus[©] questionnaire. Five of the six items from the questionnaire to be analyzed are: "Overall, how severe were your infection symptoms today?", "Overall, how were your infection symptoms today compared to yesterday?", "How much did your infection symptoms interfere with your usual activities today?", "Have you returned to your usual activities today?", "In general, how would you rate your physical health today?", and "Have you returned to your usual health today?" The scores for: symptom severity range from 0 (no infection symptoms today) to 4 (very severe); symptoms today range from 1 (much better) to 7 (much worse); symptom interference range from 1 (not at all) to 5 (very much). The first of two consecutive scores of ≤ 1 spanning at least three days and no more than five days will be considered the day of resolution, provided that no intervening scores of >1 are recorded. The scores for return to usual activities or health are either "yes" or "no", and the first occurrence of "yes" will be deemed to be day of resolution provided that a second "yes" is recorded no more than 5 days later without an intervening "no". The remaining sixth item to be analyzed is: "physical health range from 1 (poor) to 5 (excellent). The first of two consecutive scores of >4 spanning at least three days and no more than five days will be considered the day of resolution, provided that no intervening scores of <4 are recorded. Each item will be compared between treatment groups using a Cox proportional hazards model with covariates (aggregate FLU-PRO Plus[©] score for the selected five COVID-19 symptoms at baseline, serum total 25D at baseline, and body weight).

The clinical course of COVID-19 will be examined by subgroups defined by serum total 25D levels <50 ng/mL, 50 to 100 ng/mL and >100 ng/mL at Days 7, 14, 21 and 28.

 	

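### The quality-of-life time-to-resolution analyses use observed cases only and do not say how subjects who die, or stop the diary for good through severe illness, are handled; the aggregate-score endpoints from the same diary count them as unresolved.

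*SAP*

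**What the plan says.** SAP 6.2 does not impute missing quality-of-life responses. It continues: "The analysis of these items will be based on observed cases only with resolution requiring at least a three-day duration", with a pointer to SAP 5.2. That section defines how resolution is established from recorded scores but gives no censoring time. Protocol 9.2 has the same rule without the pointer. SAP 6.10.2 gives the model: "Each item will be compared between treatment groups using a Cox proportional hazards model with covariates", the covariates being baseline aggregate score, baseline 25D and body weight.

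SAP 6.2 has two other rules for the same diary:

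- Primary aggregate-score time to event: "Missing scores occurring prior to resolution are considered as lack of resolution and kept in the denominator", whatever the reason for the gap. The secondary aggregate-score endpoint has the same rule.
- Individual symptom scores: "missing results prior to resolution of symptoms due to intercurrent illness, hospitalization, or death will be imputed as lack of resolution".

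SAP 6.2 also states "No other efficacy data will be imputed" after the serum 25D imputation, so nothing elsewhere in the section fills the gap for the quality-of-life items.

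On follow-up, Protocol 6.9 says "All subjects withdrawn from treatment will continue in the study until study completion and perform all assessments unless consent is withdrawn", and Protocol 7.10 keeps the diary running after treatment: "Subject will assess and record in the diary each day at bedtime the severity of COVID-19 symptoms and quality-of-life". Neither document gives a censoring time for any time-to-resolution endpoint, or says how death enters the quality-of-life models.

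**The concern.** Endpoint 8 is meant to describe the severity and duration of illness. The subjects with the worst illness are those most likely to stop answering. If their time ends at the last completed diary, the Cox model treats them as having the same later chance of recovery as subjects still reporting. For a death that is false. For a subject too ill to resume the diary it is doubtful. If they are excluded instead, they leave the comparison altogether. Either way the result moves towards time to recovery among subjects who keep reporting.

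The symptom and quality-of-life results would also rest on different rules for the same blank diary page, with no reason given. The SAP's tipping-point analyses cover the incidence endpoints (6.2) and aggregate symptom resolution (6.10.1), not these items.

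**Working it through.** **Text.**

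| Endpoint | Model | Blank before resolution |
|---|---|---|
| Aggregate score | Cox | Unresolved, any reason |
| Individual symptoms, as of Day 10 | Logistic regression | Unresolved if due to illness, hospitalisation or death |
| Six quality-of-life items | Cox | Not imputed; observed cases |

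The aggregate score is the closest comparator, because it is also a Cox analysis. A subject held unresolved there is also censored in the end, at a time not stated. The difference is therefore how long the subject stays in the risk set, not event versus censoring.

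**Size.** The plan has no figure for the quality-of-life items, and no admission or death rates. I borrow the primary endpoint's 50% v 70% resolved by Day 28 (SAP 3.3) as an assumption. Those rates reproduce the stated hazard ratio (HR) of 1.74: ln(1 − 0.70)/ln(1 − 0.50) = 1.204/0.693 = 1.737. Assumed shares permanently lost run from 0% to 10% per arm.

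*Model A: lost subjects never recover.* A share h of each arm never resolves and leaves the diary on Days 3–10. The rest have exponential times that give 50% and 70% resolved overall. Simulation used 400,000 per arm; ranges cover follow-up to Day 28 and to Day 42.

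| Lost, placebo v active | HR, kept unresolved | HR, censored at loss | Log HR when censored |
|---|---|---|---|
| 2% v 2% | 1.73–1.74 | 1.75–1.76 | 1–3% larger |
| 5% v 2% | 1.73 | 1.69 | 4–5% smaller |
| 10% v 4% | 1.73–1.74 | 1.64–1.65 | 9–10% smaller |
| 10% v 0% | 1.72–1.76 | 1.53–1.54 | 20–25% smaller |
| 10% v 10% | 1.70–1.77 | 1.86 | 9–17% larger |
| 4% v 10% | 1.68–1.76 | 1.99–2.00 | 21–34% larger |

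Hand check of the 10% v 10% row: with the lost subjects censored early, the proportions resolved read 0.50/0.90 = 55.6% and 0.70/0.90 = 77.8%. Then ln(1 − 0.778)/ln(1 − 0.556) = 1.504/0.811 = 1.855.

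*Model B: loss is unrelated to underlying recovery time.* True HR is 1.74, times are in whole days, loss falls on Days 3–14, and follow-up runs to Day 42. With no loss the fitted HR is 1.722.

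| Lost, placebo v active | HR, kept unresolved | HR, censored | Ratio, censored/kept |
|---|---|---|---|
| 5% v 5% | 1.693 | 1.720 | 1.02 |
| 10% v 10% | 1.674 | 1.727 | 1.03 |
| 5% v 2% | 1.764 | 1.725 | 0.98 |
| 10% v 5% | 1.780 | 1.722 | 0.97 |
| 2% v 5% | 1.657 | 1.734 | 1.05 |
| 5% v 10% | 1.599 | 1.731 | 1.08 |

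The HR therefore moves by about 2–8%. With 80 per arm (1,500 runs, error about 1 point), the chance of one-sided p < 0.025, censored v kept unresolved, was 81% v 76% at 10% lost in each arm, 82% v 68% at placebo 5%/active 10%, and 84% v 88% at placebo 10%/active 5%.

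**Against sampling error.** At Day 28 there are 80 × 0.50 + 80 × 0.70 = 96 events, so SE(log HR) ≈ 2/√96 = 0.20. The 10% v 4% shift is ln 1.73 − ln 1.64 = 0.053, about a quarter of one SE.

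**The case against.** A reader might infer that the SAP censors every hospitalised subject. It does not say so. No censoring time is written, and the observed-case wording could also mean exclusion, or that resolution must be observed with everyone else followed to study end. Admission is not a censoring event either: quality of life is recorded daily until the end of follow-up, and treatment withdrawal does not stop assessments. A subject who keeps or resumes the diary stays at risk and can resolve. This stands, and it limits the point to deaths and permanent diary loss.

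A reader might also infer that one diary treats the same subject in opposite ways. That overstates it. The individual-score rule serves a Day 10 logistic regression, which must classify everyone, and the aggregate-score Cox analysis also censors unresolved subjects in the end.

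Nor is a bias of known direction shown. Model A assumes that every lost subject never recovers, and its rates are assumed for a trial that excludes severe disease at entry. In Model B, censoring leaves the HR near 1.72 and keeping subjects at risk is what moves it. Which figure is right depends on the target, which the SAP should name.

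The stakes are low. Hospitalisation, ventilation and mortality are reported separately: "Endpoint items 3-7 are all based on incidence over the entire 42 day study period". SAP 6.2 also summarises missing questionnaires before and after resolution. These are real mitigations, but they do not tell the programmer what to do with a death in a quality-of-life model.

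**Conclusion.** The point holds as a minor one. For the quality-of-life Cox analyses the plan does not count a subject who dies, or stops the diary for good through severe illness, as unrecovered, and it gives no censoring time. On the natural reading such subjects are censored informatively or dropped.

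The size is not known. If lost subjects never recover, the log hazard ratio shifts by 1–5% at 2% v 2% or 5% v 2% lost, and by roughly 20–35% only when 10% are lost in one arm and few or none in the other. If loss is unrelated to recovery, the hazard ratio shifts by about 2–8%. The sign depends on which arm loses more subjects. All of this rests on assumed loss rates and on the primary endpoint's resolution rates. With few permanent losses the effect would be small. It concerns one secondary endpoint outside the primary hierarchy and cannot alter the primary conclusions.

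**What to change.** In SAP 6.2, and in Protocol 9.2 if it is amended, replace the observed-case rule for the quality-of-life Cox models with this:

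- Responses missing before resolution because of intercurrent illness, hospitalisation or death count as unresolved on those days.
- The subject stays at risk, may still resolve on later recorded responses, and is otherwise censored at Day 42.
- Deaths before resolution are also held unresolved to Day 42.

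The second item matters: a flat classification as not resolved would misstate a subject with a short admission who later reports recovery. The SAP should also give the censoring time for subjects lost for other reasons. Keep the observed-case analysis as a sensitivity analysis.

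The cost is one sentence and one programming flag from hospitalisation and death data already collected over 42 days. Sample size, conduct and the primary hierarchy do not change. The downside is that the reason for a missing diary must be attributed, which SAP 6.2 already requires for the individual symptom scores. Some difference from the aggregate-score rule remains, because that rule counts every blank before resolution as unresolved whatever the reason.
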